### 12.2.1.2. Unconfirmed Best Overall Response

The unconfirmed best overall response is the best overall response cross visits and will be determined programmatically based on investigator assessment at each time point. Note that if the investigator assessment is non-radiologic PD by RECIST v1.1 at a time point, the overall response will be derived based on the logic specified in [Section 12.1](#). The derived overall response at that time point will be used to derive BOR.

If there are two assessments separated by not evaluable (NE) assessment(s), the best response shall be assessed applying the algorithm below, collapsing data by ignoring NE assessments.

#### **12.2.1.2.1. Unconfirmed Best Overall Response per RECIST V1.1 and irRECIST Criteria**

- To be assigned a status of SD/irSD, follow-up disease assessment must have met the SD/irSD criteria at least once after the first dose at a minimum interval of 77 days.
- If the minimum of 77 days for SD/irSD is not met, the best overall response will depend on the subsequent assessments. For example, if an assessment of PD follows the assessment of SD and SD does not meet the minimum time requirement the best response will be PD. Alternatively, subjects lost to follow-up after an SD assessment not meeting the minimum time criteria will be considered not evaluable.

#### **12.2.1.2.2. Unconfirmed Best Overall Response per irRECIST**

Besides the principles specified in [Section 12.2.1.2.1](#), irCPD and irUPD will be derived following the same principles described in [Section 12.2.1.1.2](#).

### **12.2.2. Objective Response Rate (ORR) and Disease Control Rate (DCR)**

ORR and DCR per RECIST v1.1 criteria are defined below. ORR and DCR per irRECIST criteria are defined similarly.

- ORR is defined as the percentage of subjects achieving a (confirmed) CR/PR as BOR, as assessed by the investigator per RECIST 1.1 criteria (Note that if the investigator assessment is non-radiologic PD by RECIST v1.1 at a time point, the overall response will be derived based on the logic specified in [Section 12.1](#)).
- DCR is defined as the percentage of subjects achieving a (confirmed) CR/PR, or SD as BOR, as assessed by the investigator per RECIST 1.1 criteria (Note that if the investigator assessment is non-radiologic PD by RECIST v1.1 at a time point, the overall response will be derived based on the logic specified in [Section 12.1](#)). A status of SD will be assigned if the follow-up disease assessment has met the SD criteria at least once after the date of first dose at a minimum of 77 days.
- DCR with SD durability is defined as the percentage of subjects achieving a (confirmed) CR/PR, or SD $\geq$ 161 days. A status of SD $\geq$ 161 days will be assigned if the follow-up disease assessment has met the SD criteria at least once after the date of first dose at a minimum of 161 days.

Confirmation of responses is required for the final analysis.

ORR and DCR will be reported by both RECIST v1.1 and irRECIST. An adequate assessment is defined as an assessment where the Investigator determined response is irCR, irPR, or irSD.

#### **12.2.3. Time to response (TTR)**

Time to response (TTR) is defined as the time from the first dose of study treatment to the date of the first documented irCR or irPR. Only the subset of subjects who show a

confirmed irCR or irPR from All Treated Population will be included in this analysis. TTR per RECIST v1.1 criteria is defined similarly.

Time to response will be listed.

#### **12.2.4. Duration of response (DOR)**

##### **12.2.4.1. DOR per irRECIST**

DOR will be derived and listed for subjects with a confirmed irCR or irPR. It is defined as the interval of time in months from the date of the first documented evidence of a confirmed response (irCR or irPR) to the date of first documented evidence of a confirmed disease progression according to radiological response from investigator assessment per irRECIST, or date of last adequate assessment of response, or the date of death due to any cause. An adequate assessment is defined as an assessment where the Investigator determined response is irCR, irPR, or irSD.

A summary of the assignments for progression and censoring dates for DOR per irRECIST is specified in the following table.

##### **Assignments for Progression and Censoring Dates for DOR Analysis per irRECIST:**

Situation	Date of Event (Progression/Death) or Censoring	Outcome Event (Progression/Death) Or Censored
No (or inadequate) baseline tumor assessments and the subject has not died (if the subject has died follow the rules for death indicated at the bottom of the table)	Start Date of Treatment	Censored
No post-baseline assessments and the subject has not died (if the subject has died follow the rules for death indicated at the bottom of the table)	Start Date of Treatment	Censored
Progression documented and confirmed at the next disease assessment and no less than 4 weeks apart	Date of first assessment of irPD which is confirmed consecutively	Event
Unconfirmed irPD followed by NE or another PK less than 4 weeks apart, or not further assessment,	Date corresponding irPD	Event

Situation	Date of Event (Progression/Death) or Censoring	Outcome Event (Progression/Death) Or Censored
and subject dies or discontinues from the study		
No progression (or death) or initiation of new anti-cancer therapy	Date of last 'adequate' assessment of response 	Censored
Received subsequent anti-cancer therapy prior to the date of documented events	Date of last 'adequate' assessment of response  (prior to starting initiation of therapy)	Censored
Death before first irPD assessment (or Death at baseline or prior to any adequate assessments)	Date of death	Event
Death or progression after more than one missed visit	Date of last 'adequate' assessment of response  (prior to missed assessments), refer to Section 10.2.11	Censored

1. An adequate assessment is defined as an assessment where the Investigator determined response is irCR, irPR, or irSD.
2. If irPD and New anti-cancer therapy occur on the same day assume the progression was documented first e.g., outcome is progression and the date is the date of the assessment of progression). If anti-cancer therapy is started prior to any adequate assessments, censoring date should be the start date of treatment.

#### 12.2.4.2. DOR per RECIST

DOR will be derived and listed for subjects with a confirmed CR or PR. It is defined as the interval of time in months from the date of the first documented evidence of a confirmed response (CR or PR) to the date of first documented evidence of a confirmed disease progression according to radiological response from investigator assessment per RECIST, or date of last adequate assessment of response, or the date of death due to any cause. An adequate assessment is defined as an assessment where the Investigator determined response is CR, PR, or SD.

A summary of the assignments for progression and censoring dates for DOR per RECIST is specified in the following table.

## Assignments for Progression and Censoring Dates for DOR Analysis per RECIST:

Situation	Date of Event (Progression/Death) or Censoring	Outcome Event (Progression/Death) Or Censored
No (or inadequate) baseline tumor assessments and the subject has not died (if the subject has died follow the rules for death indicated at the bottom of the table)	Start Date of Treatment	Censored
No post-baseline assessments and the subject has not died (if the subject has died follow the rules for death indicated at the bottom of the table)	Start Date of Treatment	Censored
Progression documented between scheduled visits	Date of assessment of progression 	Event
No progression (or death) or initiation of new anti-cancer therapy	Date of last 'adequate' assessment of response 	Censored
Received subsequent anti-cancer therapy prior to the date of documented events	Date of last 'adequate' assessment of response  (prior to starting initiation of therapy)	Censored
Death before first PD assessment (or Death at baseline or prior to any adequate assessments)	Date of death	Event
Death or progression after more than one missed visit	Date of last 'adequate' assessment of response  (prior to missed assessments), refer to Section 10.2.11	Censored

3. The earliest of (i) Date of radiological assessment showing new lesion (if progression is based on new lesion); or (ii) Date of radiological assessment showing unequivocal progression in non target lesions, or (iii) Date of last radiological assessment of measured lesions (if progression is based on increase in sum of measured lesions)
4. An adequate assessment is defined as an assessment where the Investigator determined response is CR, PR, or SD.
5. If PD and New anti-cancer therapy occur on the same day assume the progression was documented first e.g., outcome is progression and the date is the date of the assessment of progression). If anti-cancer therapy is started prior to any adequate assessments, censoring date should be the start date of treatment.

## 13. SAFETY ANALYSES

Unless otherwise specified, all the safety analyses will be based on the All Treated Population as defined in [Section 7](#) and summaries will include all events or assessments collected during the study. All the analyses will be performed by groups identified in [Section 9](#).

### 13.1. Extent of Exposure

Extent of exposure to GSK3174998 and pembrolizumab will be summarized separately.

The number of subjects and duration of exposure to study treatment in weeks (from first day to last day of treatment + 1 days) will be summarized. Descriptive statistics including mean, median, standard deviation, minimum, and maximum will be calculated for time on study treatment. Moreover, time on study treatment will be categorized in different time period: <3 months, 3 months to 6 months, >6 months to 12 months and >12 months.

The number of infusions administered as study treatment will be summarised with mean, median, standard deviation, minimum, and maximum.

Infusion dose intensity (the cumulative doses, divided by the total number of infusions) will be summarized using mean, median, standard deviation, minimum, and maximum. The cumulative dose is the sum of the doses administered during each infusion for a subject.

The relative dose intensity (%) of GSK3174998 is the infusion dose intensity divided by the target dose.

The number of dose delays and reasons for dose delays will be summarized.

All infusion interruptions and dose delays will be listed separately.

### 13.2. Adverse Events

AEs will be coded to the preferred term (PT) level using the Medical Dictionary for Regulatory Affairs (MedDRA dictionary) and grouped by system organ class (SOC). AEs will be graded by the investigator according to the NCI-CTCAE v4.0.

An overview summary of on-treatment AEs, including counts and percentages of subjects with the below category will be produced:

- Any AEs
- Treatment-related AEs
- AEs of special interest (AESI)
- AEs leading to discontinuation of study treatment
- AEs leading to dose reduction
- AEs leading to dose interruption/delayed
- and AEs leading to study withdrawal
- SAEs

- Treatment-related SAEs
- Fatal SAEs
- Treatment-related fatal SAEs

On-treatment AEs (or treatment-emergent AEs) include those with onset dates on or after the first study treatment dose date (this can be either GSK 3174998 or pembrolizumab). Treatment-related AE and AEs leading to discontinuation of study treatment will further be summarized by the treatment to which causality was attributed for Part 2.

Events will be summarized by frequency and proportion of total subjects, by PT. Separate summaries will be given for:

- All AEs
- Treatment-related AEs (for Part 2, the summary will include AEs related to GSK3174998 or Pembrolizumab or both)
- AEs leading to discontinuation of study treatment (for Part 2, the summary will include AEs leading to discontinuation of GSK3174998 or Pembrolizumab or both)
- AEs leading to study withdrawal
- SAEs
- Treatment-related SAEs
- AEs recorded as dose-limiting toxicities
- AESI

The summary by PT will be sorted by descending incidence.

On-treatment AEs will be summarized by the maximum grade according to the NCI-CTCAE v4.0 and sorted by PT and by PT in descending order of total incidence. The summary will use the following algorithms for counting the subject:

- **Preferred term row:** Subjects experiencing the same AE preferred term several times with different grades will only be counted once with the maximum grade.
- **Any event row:** Each subject with at least one adverse event will be counted only once at the maximum grade no matter how many events they have.

All AEs will be listed.

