9.4. Key Elements of Analysis Plan

Data will be listed and summarized according to the GSK reporting standards, where applicable. Complete details will be documented in the Reporting and Analysis Plan (RAP). Any deviations from, or additions to, the original analysis plan described in this protocol will be documented in the RAP and final study report.

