9.4.1.3. Adverse Events

AEs will be coded using the standard MedDRA and grouped by system organ class. AEs will be graded by the investigator according to the NCI-CTCAE (version 4.0).

Events will be summarized by frequency and proportion of total subjects, by system organ class and preferred term. Separate summaries will be given for all AEs, treatment-related AEs, SAEs and AEs leading to discontinuation of study treatment. AEs, if listed in the NCI-CTCAE (version 4.0) will be summarized by the maximum grade. Otherwise, the AEs will be summarized by maximum intensity.

Characteristics (e.g., number of occurrences, action taken, grade, etc) of AESI (see Section 6.3.1.3 and [Appendix 11](#)) will be summarized separately.

The incidence of deaths and the primary cause of death will be summarized.

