### 13.5. Adverse Events Leading to Discontinuation of Study Treatment and/or Withdrawal from the Study and Other Significant Adverse Events

AEs Leading to Discontinuation of Study Treatment will be summarized separately in descending order of total incidence by PT only and separate supportive listings will be generated with subject level details for those subjects:

- AEs leading to discontinuation of study treatment
- AEs leading to withdrawal from the study

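### The SAP specifies adverse-event tables by preferred term only, although the protocol calls for system organ class and preferred term, and the departure is not recorded

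*SAP*

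**What the plan says.** Protocol 9.4.1.3, which sits under Primary Analyses, sets the display: "Events will be summarized by frequency and proportion of total subjects, by system organ class and preferred term".

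SAP 13.2 uses the same sentence with a different ending: "Events will be summarized by frequency and proportion of total subjects, by PT". That sentence introduces eight separate summaries: all AEs, treatment-related AEs, those ending treatment, those ending study participation, SAEs, treatment-related SAEs, dose-limiting toxicities, and AEs of special interest (AESI). The ordering follows: "The summary by PT will be sorted by descending incidence".

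For the maximum-grade table, SAP 13.2 defines two kinds of row. One is the term row: "Subjects experiencing the same AE preferred term several times with different grades will only be counted once with the maximum grade". The other is a single overall row: "Each subject with at least one adverse event will be counted only once at the maximum grade no matter how many events they have". No row is defined at SOC level.

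SAP 13.5 is explicit for one table: "AEs Leading to Discontinuation of Study Treatment will be summarized separately in descending order of total incidence by PT only".

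SOC appears in SAP 13.2 only in the coding sentence, which still says that events are grouped by it.

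On changes between the two documents, Protocol 9.4 states: "Any deviations from, or additions to, the original analysis plan described in this protocol will be documented in the RAP". The SAP calls itself the RAP (reporting and analysis plan), so it is the document meant.

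**The concern.** AEs head the list of primary endpoints in both parts of this first-in-human study, and the protocol chose a two-level display for them. The SAP keeps the lower level and omits the upper one without comment.

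The upper level answers a question that the lower one cannot: how many subjects at this dose had any event in this class? When related events carry different terms, a PT-only table sorted by incidence scatters them over separate rows, and at small denominators each row may show one subject. The reader cannot repair this from the table, because a subject with two terms is counted in two rows.

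At stake is how clearly the final report shows clustering within a class, and any pattern across dose levels, for toxicities that have no grouped display elsewhere.

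**Working it through.** **1. The two texts side by side.**

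| Item | Protocol 9.4.1.3 | SAP 13.2 and 13.5 |
|---|---|---|
| Level of AE frequency tables | SOC and PT | PT, for all eight summaries |
| Rows in the maximum-grade table | not detailed | PT row and one overall row |
| AEs ending treatment | covered by the SOC and PT sentence | PT only, stated explicitly |
| Use of SOC | in coding and in the tables | in the coding sentence only |

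Both entries are current text, not superseded wording from an amendment log.

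**2. Is the change recorded?** The SAP neither notes nor justifies it. SAP 9 adds only that departures from the SAP itself will be identified in the study report. A table that follows the SAP would not be flagged under that rule.

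**3. Can the SOC count be recovered from the PT rows?** No. If the PT rows within a class show counts c1, c2, ..., the number of distinct subjects lies anywhere from the largest single count up to the smaller of n and the sum of the counts. Three rows of 1 in a cohort of 6 are compatible with 1, 2 or 3 subjects.

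**4. Group sizes.** Protocol 4.1.1 sets a maximum of 12 per dose level in Parts 1A and 2A, with one subject in the escalation cohort at each of the first two Part 1A levels. The Amendment 4 summary gives 9, 9 and 5 subjects for the Part 2B cohorts. SAP 8.1 displays data by dose level or cohort, so these are the denominators.

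**5. How often could scatter occur?** There is no figure in the plan to reproduce. The following is an illustration, and its inputs are assumptions that are not in the documents: true SOC-level incidence P of 20% or 33%; each affected subject reports exactly one of k equally likely terms, with k of 3 or 5. Let X be the number of affected subjects out of n. Then

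Pr(no PT row above 1 | X ≥ 2) = [ Σ C(n,x) P^x (1−P)^(n−x) · k! / ((k−x)! k^x), for x from 2 to min(n,k) ] / Pr(X ≥ 2).

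Worked case, n=6, P=0.20, k=3:
- x=2: 15 × 0.04 × 0.4096 = 0.2458, times 6/9, gives 0.1638.
- x=3: 20 × 0.008 × 0.512 = 0.0819, times 6/27, gives 0.0182.
- Numerator: 0.182.
- Pr(X ≥ 2) = 1 − 0.2621 − 0.3932 = 0.345.
- Ratio: 0.528.

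| n | P=20%, k=3 | P=20%, k=5 | P=33%, k=3 | P=33%, k=5 |
|---|---|---|---|---|
| 3 | 0.632 | 0.775 | 0.604 | 0.755 |
| 4 | 0.598 | 0.749 | 0.540 | 0.705 |
| 6 | 0.528 | 0.693 | 0.417 | 0.596 |
| 9 | 0.427 | 0.602 | 0.257 | 0.427 |
| 12 | 0.333 | 0.507 | 0.143 | 0.277 |

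These probabilities are conditional on at least two affected subjects. The joint probability, that at least two are affected and no PT row exceeds one, runs from 0.066 (n=3, P=20%, k=3) to 0.383 (n=6, P=33%, k=5) over the same grid. At n=1 an SOC row adds nothing.

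**The case against.** The strongest reply is that this is a presentation choice with limited consequences. Several parts of it stand.

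- **Other displays cover part of the ground.** Protocol Appendix 11 arranges AESI by organ group. SAP 13.2 counts subjects with any AESI in its overview, SAP 13.3 summarizes AESI characteristics separately, SAP 13.7 reports worst-case grade increases for gradable laboratory tests, and SAP 13.7.1 adds pooled hepatobiliary laboratory events and plots. All AEs are listed. This narrows the gap but does not close it. The AESI frequency table in SAP 13.2 is itself by PT, SAP 13.3 does not specify tabulation by organ group, and toxicities outside AESI and the liver tests have no grouped summary.
- **The RAP may fill in details.** Protocol 9.4.1.1 leaves full details of the safety analyses to it. But the SOC and PT display is something the protocol did state, so removing it is a departure and not a missing detail.
- **The omission may be a drafting slip.** The SAP still says that events are grouped by SOC, and its sort instruction for the maximum-grade table names the preferred term twice. That is plausible, but it is inference. For AEs ending treatment, the restriction to PT is explicit.

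Three stronger readings are tempting, and the documents do not support them.

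- A reader might infer that escalation decisions missed toxicity because of these tables. Protocol 4.1.1, 9.3 and 9.3.2 base escalation on dose-limiting toxicities, the N-CRM analysis and review of all available safety data after each cohort. The SAP is written against Amendment 4, by which time all subjects had completed treatment.
- A reader might take liver toxicity as the natural example, with enzyme rises and hepatitis merging into one SOC row. Neither document gives the dictionary mapping needed to show that these terms share an SOC, and liver laboratory events already have a pooled summary.
- A reader might conclude that a scattered toxicity will always look like isolated cases. The table above shows that this depends on how the terms split, and that it becomes less likely at n=12.

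**Conclusion.** The point holds as a low-severity inconsistency with an almost free remedy. The SAP specifies a coarser display of a primary endpoint than the protocol does and does not document the change. The consequence is confined to final reporting: related events within one SOC can appear only as single-case rows, and the PT table cannot supply subject counts per SOC.

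The textual finding needs no assumptions. The probabilities are an illustration that rests on the assumed incidences, on one term per affected subject and on equal splitting over terms. They show that scatter is plausible at these group sizes. They do not estimate how often it happened in this trial. SOC is in the coded data and subject-level listings are planned, so the information is not lost. It is only left out of the planned summaries.

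**What to change.** In SAP 13.2, produce the all-AE, treatment-related AE, SAE and maximum-grade tables by SOC and PT, as Protocol 9.4.1.3 specifies. Add to each SOC an any-event row that counts every affected subject once, at the worst grade. Keep the PT-only tables, sorted by descending incidence, as additional displays.

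Correct the sort instruction for the maximum-grade table, which names the preferred term twice. If any table is deliberately left PT-only, such as the one in SAP 13.5 for AEs ending treatment, record it in the SAP as a departure from the protocol and give the reason.

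This is a free improvement. Events are already coded to SOC, no new data or analysis population is needed, and the only cost is longer tables.

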4.1.1. Dose Escalation

For the first two dose levels (see [Table 2](#)), an accelerated titration design is planned with one subject enrolled at each of these dose levels. Each subject must complete the 4 week DLT evaluation period and the available safety data must be reviewed before a decision is made on whether to proceed to the next dose level. If a subject experiences a DLT, then this will trigger the implementation of the modified 3+3 design as shown in [Table 1](#). If a subject withdraws from the study before the completion of the 4 week DLT evaluation period for reasons other than DLT, the subject will be replaced.

For subsequent dose levels, a modified 3+3 design will be used for dose escalation as shown in [Table 1](#). The first three subjects treated at the third dose level will begin treatment 1 week apart to allow assessment of initial safety data in each subject before beginning the next subject's treatment. Evaluation of the available safety data over the first 4 weeks of treatment is required from at least 3 subjects before a decision is made whether to enroll additional subjects at the same, or the next higher dose level. Subjects who withdraw from the study before the completion of 4 weeks treatment and 2 doses for reasons other than DLT may be replaced. After the third dose level cohort is completed, subsequent dose levels may initially enroll up to 4 subjects and subjects will begin treatment at least one calendar day apart.

If 1 of 3 (or 1 of 4) subjects experiences a DLT at a particular dose level, additional subjects will be enrolled at that dose level so that a total of 6 subjects are treated at that dose level. If at least 2 of 6 subjects experience a DLT at a particular dose level, a lower (or intermediate) dose level may be explored to better define the MTD. The Steering Committee may propose that a given dose-escalation cohort be expanded up to a total of 12 subjects if (i) further evaluation of the frequency of a given toxicity is warranted, based upon the observed safety profile in the 6 subjects already recruited in the cohort or (ii) further evaluation of pharmacodynamic markers to aid dose selection is warranted; in either case, the incidence of confirmed DLT must not exceed 33%. Dose-escalation decisions will be documented in writing with copies maintained at each site and the study files.

Table 1 3 + 3 Dose-Escalation Guidelines

Number of Subjects with DLT at a Given Dose Level	Action ^a

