0 out of 3 subjects	Escalate to next dose level and enter 3 subjects
1 out of 3 subjects	Accrue 3 additional evaluable subjects at current dose level for a total of 6 evaluable subjects
1 out of 6 subjects	Escalate to next dose level
2 or more subjects in a dosing cohort (up to 6 subjects)	Dose escalation will be stopped. At this dose level, the MTD has been exceeded (highest dose administered).

a. The Steering Committee may propose that a given dose-escalation cohort be expanded up to a total of 12 subjects if (i) further evaluation of the frequency of a given toxicity is warranted, based upon the observed safety profile in the 6 subjects already recruited in the cohort or (ii) further evaluation of pharmacodynamic markers to aid dose selection is warranted; in either case, the incidence of confirmed DLT must not equal or exceed 33%.

DLT = Dose-limiting toxicity; MTD = Maximum tolerated dose

In alignment with the guidance prospectively established in the Protocol (see above), the Steering Committee proposed that dose-escalation cohorts be expanded up to a total of 12 subjects in order to further evaluate pharmacodynamic markers to aid dose selection. This proposal was agreed and implemented at the time of opening Cohort 4 (0.1 mg/kg) and documented in writing. Since the incidence of confirmed DLT must not exceed 33% in this study, the recommended dose from a Continuous Reassessment Method (N-CRM) analysis [Neuenschwander, 2008] will be calculated (as prospectively described in Section 9.3). The N-CRM is a type of Bayesian adaptive dose-escalation scheme. The method is fully adaptive and makes use of all the DLT information available at the time of each dose assignment.

From Part 1 Cohort 4 (0.1mg/kg) onwards and for all Part 2 dose levels, each dose level may initially enroll up to 4 subjects. Once at least 3 of these subjects have completed the DLT evaluation period (4 weeks), a decision may be made to initiate the next higher dose level, pending the evaluation of safety data using the N-CRM methodology. Subjects identified as eligible for enrollment after the enrollment of 4 subjects in current dose level and before next higher dose level is open may be assigned to a lower dose level.

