## 7. ANALYSIS POPULATIONS

### 7.1. All Treated Population

The **All Treated Population** is defined as all subjects who receive at least one dose of GSK3174998. Safety and anticancer activity will be evaluated based on this analysis population.

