## 9. GENERAL CONSIDERATIONS FOR DATA ANALYSES

SAS 9.3 or higher version will be used to perform all data analyses, generate tables, figures, and listings. The exception would be CRM analyses, which are specified to take place in FACTS.

All data within scheduled visits up to the time of study completion/withdrawal from study will be included in the analysis summaries, regardless of duration of treatment. Unscheduled visits will be considered for most extreme result reporting (e.g. worst grade post-baseline) and included in data listings.

Actual treatment derivation is specified in [Section 10.2.10](#). Planned treatment is collected on dosing regimen eCRF page.

Efficacy analysis will be based on planned treatment.

For Part 1 and Part 2A, Safety and PK analysis will be based on actual treatment the subjects received and displayed by dose level. Efficacy analysis will be based on planned treatment and displayed by dose level.

For Part 2B, tables and figures will be displayed by cohort type. The subject will be summarized in the cohort type though the actual dose level may be different from the planned dose level. A footnote will be added in the Safety and PK table or figure to explain the discrepancy.

Unless otherwise noted, Safety and PK listings will be based on the actual treatment and efficacy listings will be based on the planned treatment.

In addition, for PK and receptor occupancy analysis, if a subject received different doses of treatment, the subject will be excluded from the analysis.

Deviations from the analyses in the RAP will be identified in the CSR.

Unless otherwise noted, the denominator for the percentage is the number of subjects in the analysis population used for the summary.

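### SAP 13.2 reports DLTs, a primary endpoint, only as a share of All Treated subjects; the DLT-evaluable denominator by dose level should be added

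*SAP*

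**What the plan says.** SAP Section 2.1 names DLT among the primary endpoints for Part 1 and Part 2. The only DLT output is one item in the list of separate summaries in SAP 13.2: "AEs recorded as dose-limiting toxicities". The sentence that introduces the list fixes the format: "Events will be summarized by frequency and proportion of total subjects, by PT". On-treatment events "include those with onset dates on or after the first study treatment dose date"; no 28-day limit is set for the DLT item.

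SAP Section 13 bases safety analyses on the All Treated Population, which "is defined as all subjects who receive at least one dose of GSK3174998" (Section 7.1). Section 9 adds that, unless noted otherwise, "the denominator for the percentage is the number of subjects in the analysis population used for the summary". It also says that Part 1 and Part 2A safety results are shown by dose level. The only other population is the PK Population.

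Protocol 4.1.1 works from a different count. Table 1 answers one DLT in three subjects with "Accrue 3 additional evaluable subjects at current dose level for a total of 6 evaluable subjects". On early leavers the text says: "Subjects who withdraw from the study before the completion of 4 weeks treatment and 2 doses for reasons other than DLT may be replaced". Protocol 4.3 gives a similar replacement rule with 4 weeks only and no second-dose condition. For Part 1 from Cohort 4 and for all of Part 2A, Section 4.1.1 gives the DLT evaluation period as 4 weeks. The same section states that "the incidence of confirmed DLT must not exceed 33% in this study".

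**The concern.** The protocol's escalation table uses evaluable subjects, while the SAP reports the DLT endpoint over everyone dosed. A subject who leaves in week 2 for progression and is replaced adds nothing to the Table 1 count but adds one to the SAP denominator. With three to six subjects in most escalation cohorts, one such subject visibly changes the percentage, and the change goes in one direction. A reader of the planned table would see neither how many subjects were observed for the full DLT period nor whether any were replaced. At stake is whether a primary safety endpoint is reported on the subjects who could inform it.

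**Working it through.** **Inputs.** Protocol 4.5.3 (cut-off 13 August 2019) gives 1 DLT in 4 dosed at 10 mg/kg plus pembrolizumab, 1 DLT in 9 dosed at 0.03 mg/kg plus pembrolizumab, and no DLTs on monotherapy. These are counts of subjects dosed. The number of non-evaluable subjects, k, appears nowhere in the documents, so it is an assumption shown as a range. The SAP states no DLT rate to reproduce.

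**Direction.** Let d be the number of subjects with a DLT in Days 1-28, N the number treated and N - k the number evaluable. Replacement applies only to subjects who leave for reasons other than DLT, so all d subjects are among the N - k. Because N - k ≤ N, d/N ≤ d/(N - k). The planned rate is therefore equal to or below the evaluable rate. This assumes the same d in both rates; the planned summary has no Day 28 limit, so a later event flagged as a DLT would add to its numerator.

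**Size at 10 mg/kg plus pembrolizumab** (exact Clopper-Pearson 95% limits):
- k = 0: 1/4 = 25.0% (0.6% to 80.6%)
- k = 1: 1/3 = 33.3% (0.8% to 90.6%)
- k = 2: 1/2 = 50.0% (1.3% to 98.7%)

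**Size at 0.03 mg/kg plus pembrolizumab:**
- k = 0: 1/9 = 11.1% (0.3% to 48.2%)
- k = 1, 2, 3: 1/8 = 12.5%, 1/7 = 14.3%, 1/6 = 16.7%
- Reaching 33.3% needs 1/(9 - 6), that is, six of the eight subjects without a DLT non-evaluable.

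**Monotherapy:** 0/N = 0/(N - k) = 0, so the denominator does not change the estimate.

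**How likely is k ≥ 1 at 10 mg/kg?** The documents give no rate. If each of the three subjects without a DLT independently had probability q of being non-evaluable, the chance of at least one is 1 - (1 - q)³: 14.3%, 27.1% and 48.8% for q = 5%, 10% and 20%. These values of q are assumptions only. The confidence limits also show how little four subjects say about the true rate on either denominator.

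**The case against.** The SAP follows the protocol here. Protocol 9.3.1 and 9.4.1.1 prescribe the All Treated Population for safety, and the protocol defines no DLT-evaluable population. That stands: this is a reporting choice that can be improved, not a contradiction between the documents.

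A reader might infer that moving from 25.0% to 33.3% crosses the 33% limit and so changes the MTD or MAD. The documents do not support that:
- Section 4.1.1 treats 1 of 3 and 1 of 4 alike: enrol to 6.
- Table 1 declares the MTD exceeded only at two or more DLTs.
- Escalation in Part 2 also draws on the N-CRM, which under SAP 5.2 uses DLT information from all enrolled subjects.
- 10 mg/kg is the highest planned level, and the final MTD rests on the full safety and tolerability record.

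A reader might also infer that Part 2 events excused under Protocol 4.1.4 (Grade 3 or higher, known with pembrolizumab, controlled within 2 weeks) would go unreported. They would be missing from the DLT summary, but SAP 13.2 lists every AE, and most should also be in the separate AESI listing (SAP 13.3, Protocol Appendix 11). What is lacking is a display limited to the DLT window. No data field for use of the exemption is described, so a listing could not reliably isolate those events.

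Finally, the replacement sentence might be read as making two doses a condition of evaluability. It concerns subjects who withdraw. Table 4 footnote a foresees steroid use delaying dose 2 without a DLT. A subject observed for 28 days with a late second dose should stay in the denominator.

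None of this removes the one-sided difference between the two denominators.

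**Conclusion.** The point holds as a matter of unbiased reporting. The SAP's single DLT summary uses a denominator that can include subjects not observed for the DLT period, so for the same Days 1-28 DLTs it can equal or understate the evaluable rate. On the reported counts the only sensitive level is 10 mg/kg plus pembrolizumab: 25.0% if all four were evaluable, 33.3% if one was not. No non-evaluable subject is documented, so the actual difference may be zero. The conclusion does not extend to the MTD or MAD, or to escalation decisions already taken. It is a cheap improvement worth making because DLT is a primary endpoint. Confidence is medium, because the size depends on a count that the documents do not give.

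**What to change.** In SAP Section 7, define a DLT-Evaluable Population: Part 1A and Part 2A subjects who had a recorded DLT in Days 1-28 or who completed the 4-week DLT evaluation period. Do not require a second dose; footnote any subject whose dose 2 was missed or delayed.

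In SAP 13.2, add one table by part and dose level with N treated, N evaluable, n with a DLT, and n/N evaluable. Keep the planned All Treated summary.

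Optionally, list Part 2 treatment-related events of Grade 3 or higher with onset in Days 1-28, with a yes/no DLT flag. Do not label it a listing of exempted events, because it would also hold events that never met Table 4.

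The protocol's DLT definition stays as it is, and no event is re-adjudicated. The cost is one population, one table and, if wanted, one listing, built from exposure, disposition and AE data already collected. It should go in before Database Freeze; after that, the CSR can report it as a deviation, as SAP Section 9 provides.
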